11.7.1.8 EuroQol 5-dimension health questionnaire 5-level (EQ-5D-5L)

EQ-5D-5L is a standardised measure of health status developed by the EuroQoL group to provide a simple, generic measure of health for clinical and economic appraisal (Greiner et al. 2003). The EQ-5D-5L is a self-administered questionnaire used to assess health status 'today' and is divided into 2 sections. The first section includes 5 dimensions (mobility, self-care, usual activity, pain/discomfort, and anxiety/depression); each dimension will be assessed by the subject using a 5-point Likert scale ('no problems', 'slight problems', 'moderate problems', 'severe problems', and 'extreme problems'). The second section consists of a vertical visual analogue scale anchored at 0 ('the worst health you can imagine') and 100 ('the best health you can imagine'). The EQ-5D-5L will be completed at the trial site according to the schedule of trial procedures in Section 4.

11.7.1.9 Work Limitation Questionnaire (WLQ)

WLQ is a validated questionnaire to measure the degree to which health problems interfere with specific aspects of job performance and the productivity impact of these work limitations (Lerner et al. 2001). It asks subjects to rate their level of difficulty or ability to perform 25 specific job demands in the last 2 weeks. Responses to the 25 items are combined into 4 work limitation scales: time management, physical demands, mental/interpersonal, and output demands. These capture the multidimensionality of job roles and also reflect an important characteristic of many chronic illnesses, in that they may result in limitations in performing some activities but not others. Scale score range from 0 ('limited none of the time') to 100 ('limited all the time'). The WLQ will be completed at the trial site for subjects with a paid job according to the schedule of trial procedures in Section 4.

11.7.1.10 Treatment Satisfaction Questionnaire for Medicine (TSQM)

The TSQM v. II is a generic questionnaire assessing subject's satisfaction with the treatment (Atkinson et al. 2004). The tool consists of 11 items addressing four domains (effectiveness, side effects, convenience and overall satisfaction). Ten items will be assessed by the subject using a 7-point scale ('extremely dissatisfied', 'very dissatisfied', 'dissatisfied', 'somewhat satisfied', 'satisfied', 'very satisfied', and 'extremely satisfied'). However, one item will be assessed using a 2-point scale ('yes' and 'no'). The score ranges from 0 to 100 with higher scores indicating higher satisfaction. The TSQM will be completed at the trial site according to the schedule of trial procedures (Panel 2).

11.7.2 Atopic dermatitis lesions on scalp

Subjects with AD lesions on scalp are not allowed to enter the trial and if AD lesions occur on the scalp during the trial these should not be treated with IMP.

Whether subjects have AD lesions on scalp will be captured in the eCRF as specified in the schedule of trial procedures (Section 4).

11.8 Estimate of total blood volume collected

Blood samples will be drawn for haematology, biochemistry, serology, PK, and serum pregnancy test (females of childbearing potential only). The total volume of blood to be drawn is approximately 39 mL.

11.9 End of trial

An end of trial form must be completed in the eCRF for all randomised subjects (including subjects who permanently discontinue IMP and subjects who withdraw from trial). The following data will be collected:

- Whether the subjects completed the trial.
- Last trial site visit or contact number for which data is recorded.
- Date and time of last application of IMP.
- Primary reasons for discontinuation from IMP, withdrawal from trial, and not attending primary endpoint visit, if applicable (lack of efficacy, AE, withdrawal by subject, lost to follow-up, pregnancy, death, other).

The end of trial form will be completed when the subject has had their last visit (at the early termination visit, the safety follow-up visit, or the primary endpoint visit, whichever comes last).

11.10 Storage of biological samples

PK samples and skin biopsies will be retained for as long as the quality of the material permits evaluation but for no longer than 12 months after completion of the CTR unless specific additional consent has been obtained that allows storage for future research (see below).

Biobank

This protocol includes the collection and analysis of different biological samples. If consent is given by the subject, LEO will store skin biopsies and skin swabs collected in a biobank established by LEO and hosted by BioStorage Technologies GmbH. The residual biological samples will be used for future research performed by LEO. Donation of the samples for future research is voluntary and subjects must give their separate written consent to confirm donation and storage and the terms associated herewith. The samples will be transferred from the relevant laboratory to the biobank. The samples will be labelled with the trial ID, subject ID, and the sample date to protect the privacy of the subjects and to allow continued blinding for future analyses. The samples from this trial will be stored in the biobank for up to 10 years after the end of the trial and will then be destroyed.

12 Scientific rationale for trial design and appropriateness of assessments

This is a multi-centre, randomised, vehicle-controlled, double-blind, parallel-group trial, which will be conducted in accordance with the protocol, ICH-GCP and applicable regulatory requirements.

The trial will be conducted at multiple trial sites located in North America (USA and Canada) and Australia. High-quality trial sites with shared standards of practice and values will be selected.

Patients with AD represent a heterogeneous patient population with disease severity ranging from mild to severe. To mitigate any potential difference in trial outcome based on baseline characteristics, eligibility criteria for inclusion have been carefully selected and trial subjects will be randomised in stratified manner as described in Section 9.3. The randomisation will minimise selection bias and minimise influence of (intrinsic) confounding factors and the stratification will ensure a certain balance of the treatment groups with respect to disease severity and region.

The most important inclusion criteria for entry into the trial is a diagnosis of AD (as defined by the Hanifin and Rajka 1980 criteria ([Hanifin & Rajka 1980](#), [Appendix 6](#)) and history of AD for at least 1 year, to ensure correct diagnosis and rule out differential diagnosis.

The inclusion of 4 active treatment arms with 1, 3, 8 and 20 mg/g of delgocitinib cream and a vehicle control group is considered enough to establish a dose-response signal. The vehicle control group will serve as reference and has been added to establish the efficacy and safety of the delgocitinib cream in a blinded trial design.

The trial endpoints have been selected to evaluate the efficacy of delgocitinib in improving the severity and extent of AD. EASI, vIGA-AD and SCORAD will be used in this clinical trial as investigator-rated assessments of disease severity. EASI is a validated measure used in clinical practice and clinical trials to assess the severity and extent of AD ([Hanifin et al. 2001](#), [Tofte et al. 1998](#)). vIGA-AD is a validated instrument used in clinical trials to assess the subject's global AD and SCORAD is a validated tool to assess the extent and severity of AD lesions and subjective symptoms ([European Task Force on Atopic Dermatitis 1993](#)). The primary endpoint of the trial is to evaluate the change in EASI score from baseline to Week 8. The trial endpoints will also address subject's perception of disease severity and the impact on sleep, daily activity, and health-related quality of life, and safety.

The duration of this trial is 8 weeks. This duration - based on results from a phase 2a trial in adults with the ointment formulation ([Nakagawa et al. 2018](#)) - is considered to be sufficient to evaluate the duration required for optimal treatment effect.

13 Adverse events

13.1 Definition and classification of adverse events

AEs and SAEs are defined in [Appendix 1](#).

Classification of AEs in terms of severity, causality and outcome is defined in [Appendix 2](#).

13.2 Collection of adverse event reports

AEs must be collected from time of first trial-related activity after the subject has signed the ICF until completion of the clinical trial for the individual subject (defined as safety follow-up visit 2 weeks after the last IMP administration).

AEs must be assessed by medically qualified personnel.

At all visits, the subject will be asked a non-leading question by the investigator about AEs, for example: “How have you felt since I saw you last?” No specific symptoms should be asked for. It is important that the investigator also observes the subject for any changes not reported by the subject and records these changes. If a subject report an AE during the phone call on Day 4, it is up to the investigator’s discretion to perform an unscheduled visit.

Refer to Sections [11.4.1](#) to [11.4.4](#) for principles for data entry in the eCRF.

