- b) If the date of a trial visit does not conform to the clinical trial protocol, subsequent visits should be planned to maintain the visit schedule relative to baseline/randomisation at Day 1

- c) A visit at the trial site is not required on Day 4, a member of trial site personnel will call the subjects
- d) End of treatment assessments will be conducted at Week 8. Early termination: subjects, who discontinue IMP treatment prior to Week 8 or withdraw from trial will be asked to return to the trial site for end of treatment assessments at an early termination visit as soon as possible after the last IMP application for completion of all trial procedures scheduled for the visit at Week 8 (except for the skin biopsy, if the subject has consented to have skin biopsies obtained), and they will also be asked to return to the trial site 2 weeks after the last IMP application for a follow-up visit and at Week 8 for a primary endpoint visit
- e) All subjects will be asked to return to the trial site approximately 2 weeks after the last IMP application for assessment of safety at a follow-up visit
- f) Subjects who discontinue IMP treatment prior to Week 8 will be asked to return to the trial site at Week 8 for a primary endpoint visit
- g) Unscheduled visits may occur if subjects need to make a visit in between the scheduled visit dates due to an AE, difficulty complying with the trial protocol requirements, or a significant change in their disease state
- h) The informed consent form(s) must be signed prior to performing any protocol related procedures, including but not limited to screening evaluations and alteration of ongoing treatments unless medically justified
- i) All returned IMP tubes will be weighed by the CMO
- j) Relevant prior/concomitant medication should be included from 6 months prior to Day 1 (baseline) until end of trial
- k) Relevant medical history must be recorded from the subject's birth. In case medical history is incomplete at screening visit, missing data will be retrieved at Day 1 (baseline)
- l) BSA is assessed as a part of SCORAD
- m) Completion of the eDiary will be initiated at the latest 1 week prior to Day 1 (baseline). Compliance with the eDiary completion will be reviewed by the trial site staff throughout the trial.
- n) Only for subjects with a paid job.
- o) Subjects do not have to be fasting for safety laboratory samples

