Other objectives	Other endpoints

To compare the safety of twice daily applications of delgocitinib cream 1, 3, 8, 20 mg/g with delgocitinib cream vehicle for 8 weeks in the treatment of subjects with mild to severe AD.
 
To evaluate the health-related quality of life and efficacy of twice daily applications of delgocitinib cream 1, 3, 8, 20 mg/g and delgocitinib cream vehicle for 8 weeks in the treatment of subjects with mild to severe AD.
	
Safety
 
 • Number of AEs. 
Health-related quality of life and efficacy
 
 • EASI50 at Week 8. • EASI90 at Week 8. • SCORAD50 at Week 8. • SCORAD75 at Week 8. • Change in SCORAD from baseline to Week 8. • Change in ADSD (weekly average for each individual symptom) from baseline to Week 8. 
 ○ Reduction in worst pruritus (“itch” – one of the symptoms captured in ADSD) (weekly average) of ≥ 4 points from baseline to Week 8 among subjects with baseline worst pruritus (weekly average) ≥ 4. • Change in Eczema-related Sleep NRS (weekly average) from baseline to Week 8. • Reduction in DLQI of ≥ 4 point from baseline to Week 8 among subjects with baseline DLQI ≥ 4. • Change in DLQI score from baseline to Week 8. • Change in POEM from baseline to Week 8. • Change in EQ-5D-5L from baseline to Week 8. • TSQM at Week 8. • Change in WLQ from baseline to Week 8.

Objectives	Endpoints

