9.5 Rescue treatment

If medically necessary (i.e. to control intolerable AD symptoms), rescue medication for AD may be provided to trial subjects at the discretion of the investigator. The investigators should make every attempt to conduct efficacy and safety assessments (for example disease severity scores, safety laboratory assessments) immediately before administering any rescue treatment.

If rescue medication is initiated, the subject must stop treatment with IMP immediately and must not restart treatment with IMP. It must be stated in the eCRF that the subject receives rescue medication.

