14.3.3 Exposure and treatment compliance

The duration of exposure to treatment in a specific visit interval will be calculated as the number of days from date of first application of IMP in that period to the date of last application of IMP in that period, both days included.

Exposure to treatment will be presented for the safety analysis set as days of exposure per treatment group.

Drug accountability data will be calculated by subtracting the weight of the used tubes from the mean normal weight of full tubes. Average weekly/bi-weekly and total usage will be presented per treatment group, respectively, both for time intervals between visits (1 or 2-week periods depending on the time between site visits) and total period.

Adherence to treatment regimen will be recorded in the eCRF. If any complications or deviations in administration are observed, these will be described as protocol deviations.

Adherence will be presented for the safety analysis set for each treatment group via the percentage of applications missed.

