14.3.9.1 Adverse events

AEs will be coded during the course of the trial according to MedDRA. AEs will be presented by preferred terms and primary SOC.

Treatment-emergent AEs will be summarised; however, all AEs recorded during the course of the trial will be included in subject data listings. An event will be considered treatment-emergent if started after the first use of IMP or if started before the first use of IMP and worsened in severity after first dose of IMP. The tabulations described in the following will only include the treatment-emergent events. In each of the tabulations, AEs are defined by MedDRA preferred terms within primary SOC.

An overall summary of the number of events and the number (percentage) of subjects with any treatment-emergent AEs, deaths, SAEs, premature discontinuations from the trial due to AEs, treatment-related AEs and severe AEs will be presented.

The number of AEs and number of subjects with each type of AEs will be tabulated by treatment group.

The severity for each type of AE will be tabulated by treatment group. Where there are several recordings of severity for a given type of AE, severity will be taken as the most severe recording for that AE.

The causal relationship to IMP for each type of AE will be tabulated by treatment group. Where there are several recordings of causal relationship to the IMP for a given type of AE, causal relationship will be taken as the most-related recording from the last report of that AE, since that is when the investigator will be in possession of most information and therefore be best able to judge causal relationship.

Related AEs are defined as AEs for which the investigator has not described the causal relationship to IMP as 'not related'. The number of subjects with each type of related AE will be tabulated.

SAEs will be evaluated separately and a narrative for each will be given.

Adverse events of special interest will be tabulated by treatment group and listed.

AEs leading to withdrawal from trial and AEs leading to permanent discontinuation of IMP will be tabulated by treatment group and listed.

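### AE observation time depends on when each subject stops IMP, but the arms are compared only by raw counts and percentages, so unequal early stopping can distort the safety comparison in either direction

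*Combined protocol and SAP*

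**What the plan says.** The safety objective in Section 6, Panel 3 is comparative: "To compare the safety of twice daily applications of delgocitinib cream 1, 3, 8, 20 mg/g with delgocitinib cream vehicle for 8 weeks". Its only endpoint is the number of AEs.

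Section 13.2 collects AEs from the first trial-related activity after consent "until completion of the clinical trial for the individual subject (defined as safety follow-up visit 2 weeks after the last IMP administration". In the schedule (Section 4, Panel 2) that visit falls at Week 10 for a completer. For a subject who stops early it comes sooner.

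Panel 2 also marks AE collection at a separate primary endpoint visit. Under its footnote f, subjects who stop IMP before Week 8 "will be asked to return to the trial site at Week 8 for a primary endpoint visit". Section 14.3.9.1 puts no upper time limit on treatment emergence: "An event will be considered treatment-emergent if started after the first use of IMP". An AE first recorded at that visit would therefore count.

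Early stopping is tied to outcome. Section 9.5 says: "If rescue medication is initiated, the subject must stop treatment with IMP immediately and must not restart treatment with IMP". Section 10.1 lists lack of efficacy and adverse events among the reasons for stopping, and subjects who stop are not replaced.

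The AE analysis in Section 14.3.9.1 consists of "An overall summary of the number of events and the number (percentage) of subjects with any treatment-emergent AEs" and certain subsets, followed by tables by AE type: "The number of AEs and number of subjects with each type of AEs will be tabulated by treatment group". Section 14.3.3 adds: "Exposure to treatment will be presented for the safety analysis set as days of exposure per treatment group". Nothing links those days to the AE tables.

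**The concern.** A count or a crude percentage compares arms fairly when subjects are observed for about the same time. Here each subject's window moves with the date of last application, and that date can depend on arm. A vehicle subject may need rescue and have to stop; a subject on an active strength may stop because of an AE. Two arms with the same AE rate per week can then show different counts and percentages, and two arms with different rates can look alike.

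Section 5.3 says the results will support dose selection for phase 3. The comparison with vehicle is part of that evidence, and with 50 subjects per arm a few events can change how a table reads.

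The conflict over when AE collection ends adds a second problem. If sites read it differently, early stoppers will have different windows even within one arm.

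**Working it through.** The plan states no AE rate and no discontinuation rate, so there is no figure of its own to reproduce. The calculation below shows a range under stated assumptions.

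**Inputs from the documents.** Completers are observed from Day 1 to the Week 10 follow-up visit (Panel 2), taken as 10 weeks. Under Section 13.2 an early stopper is observed for stop week + 2. If the Panel 2 visit is attended, observation runs to Week 8. The two readings differ whenever stop week + 2 < 8, that is, for stops before about Week 6. There are 50 subjects per arm (Section 7.2).

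**Assumptions.** Early stoppers stop at Week 3, so they are observed for 5 weeks (Section 13.2) or 8 weeks (Week 8 visit attended). The proportion stopping early, d, is 15%, 25% or 40% on vehicle and 5% on active. The true AE rate is constant and equal in both arms, with no AD-worsening effect for now.

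**Mean observation time** = (1 − d) × 10 + d × w, with w = 5 or 8. With equal rates, expected counts are proportional to it.

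| Early stops, vehicle vs active | Mean weeks, Section 13.2 | Active/vehicle count | Mean weeks, to Week 8 | Active/vehicle count |
|---|---|---|---|---|
| 15% vs 5% | 9.25 vs 9.75 | 1.054 | 9.70 vs 9.90 | 1.021 |
| 25% vs 5% | 8.75 vs 9.75 | 1.114 | 9.50 vs 9.90 | 1.042 |
| 40% vs 5% | 8.00 vs 9.75 | 1.219 | 9.20 vs 9.90 | 1.076 |

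**Percentages are affected too.** With an assumed first-AE hazard of 0.05 per week, the proportion with any AE is (1 − d)(1 − e^(−0.05×10)) + d(1 − e^(−0.05×w)). For 25% vs 5% stopping this gives 35.0% vs 38.5% under Section 13.2, and 37.8% vs 39.0% with follow-up to Week 8. There is no true difference.

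**Size against chance.** At an assumed 0.10 AEs per week and 25% vs 5% stopping, expected counts under Section 13.2 are 50 × 0.10 × 8.75 = 43.75 on vehicle and 50 × 0.10 × 9.75 = 48.75 on active, a gap of 5.0. The Poisson SD of the difference is √(43.75 + 48.75) = 9.6. With follow-up to Week 8 the counts are 47.5 and 49.5, a gap of 2.0.

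**The opposing effect.** Section 13.6.6 requires clinically significant worsening of any condition, the trial disease included, to be reported as an AE. Each Week 3 stopper loses 10 − 5 = 5 weeks of observation. At 0.05 to 0.15 AEs per week that is 0.25 to 0.75 expected AEs. If a larger fraction of early stoppers than this has one extra AD-worsening AE recorded, the arm with more stoppers shows more AEs, not fewer. With follow-up to Week 8 the loss is 2 weeks and the break-even fraction is 10% to 30%. Example under Section 13.2, at 0.10 per week and 25% vs 5% stopping, with 75% of stoppers having such an AE: vehicle 43.75 + 50 × 0.25 × 0.75 = 53.1; active 48.75 + 50 × 0.05 × 0.75 = 50.6.

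**What a rate does.** Dividing by observation time returns a ratio of 1.00 in every row of the table, because the rate was assumed constant. If instead all AEs fell in the first 5 weeks, raw counts would be equal, and in the 25% vs 5% row under Section 13.2 the rate would be 9.75/8.75 = 1.11 times as high on vehicle. A rate alone can therefore mislead too.

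**The case against.** A reader might infer that the vehicle arm must show fewer AEs, and that the active strengths will look less safe than they are. The documents do not support that. Section 13.6.6 makes worsening AD an AE, and Appendix 1 includes the reasons for an unfavourable, unplanned change in medication. Rescue for intolerable symptoms would often bring an AE with it, which pushes the vehicle count up. A strength with many AE-driven stops would have its own later events under-counted. This part of the objection stands: the direction is unknown.

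It also stands that the Section 13.2 figures are the larger end of the range. Panel 2 collects AEs at Week 8, and Section 13.2 itself has the AE question asked at every visit. Attendance shrinks the effect to 2–8% on the same assumptions. It does not remove it, since Week 8 is still two weeks short of a completer's window. Section 10.3 names only the early termination visit for subjects who withdraw from the trial, although Panel 2 footnote d asks them back for the later visits as well.

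Finally, counts are not the only output. Percentages, discontinuation reasons (Section 14.3.1) and exposure days (Section 14.3.3) are shown by arm, and no formal AE test is described. Unequal stopping will be visible. But a reader could not correct the AE tables from those displays: the percentages share the problem, and treatment exposure is not the time over which AEs were collected. Extra AD-worsening events also do not restore the unobserved weeks for infections or other event types, which are tabulated separately.

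**Conclusion.** The point holds in a limited form. AE observation time depends on when each subject stops IMP, Section 13.2 and Panel 2 disagree on when collection ends for early stoppers, and no planned AE summary allows for observation time. Unequal early stopping can therefore distort the comparison with vehicle, in a direction that cannot be known in advance.

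With no AD-worsening effect, the active count would be about 5%, 11% or 22% higher under Section 13.2, and about 2%, 4% or 8% higher with follow-up to Week 8. These figures rest on assumed stopping proportions, an assumed Week 3 stop and a constant, equal AE rate; none of these is stated in the documents. In the worked example the shift is smaller than chance variation between two arms of 50, but unlike chance it follows from how long subjects are observed. The claim that the active strengths will look worse is not established. This is a modest and inexpensive improvement, not a flaw that invalidates the safety analysis.

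**What to change.** 1. Reconcile Section 13.2 with Panel 2, so that both state the same end of AE collection for subjects who stop IMP early, including those who withdraw from the trial.
2. In Section 14.3.9.1, add by arm, beside each raw number and percentage, the events and the subjects with events per patient-years of observation. Observation runs from first IMP to the end of AE collection for that subject; it is not the exposure time of Section 14.3.3. Read the rates together with the raw figures when comparing each strength with vehicle.
3. Show the overall AE summary with and without worsening of AD.

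The cost is some wording and wider tables. The dates needed are already recorded, and Section 14.3.12 has the statistical analysis plan finalised before the code is broken. Because the rates assume a roughly constant AE hazard, they should supplement the raw counts, not replace them.
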